6.3.3. Mixed Model for Repeated Measures (MMRM)

An MMRM method can be justified based on the hypothetical strategy (ICH E9 R1) for handling intercurrent events. In this strategy the effect of study treatment is assessed in a hypothetical trial where all patients have complete data and continue to take study treatment without dropping out of the study. The MMRM method assumes that missing data can bias results, but the bias can be attenuated by modeling random effects using the within-subject error correlation structure. These correlations between the repeated measurements provide the platform used to account for the bias from subject dropout by assuming the dropout follows missing at random (MAR) assumption.

Selected efficacy and health outcomes variables will be assessed using MMRM as a supplementary analysis. The details are described in [Table JAHV.6.5](#).

6.4. Multicenter Studies

This study will be conducted by multiple investigators at multiple sites internationally. The countries will be categorized into geographic regions, as described in [Table JAHV.6.2](#).

6.5. Multiple Comparisons/Multiplicity

No multiplicity control measures will be used.

6.6. Patient Disposition

An overview of patient disposition will be summarized by treatment periods with the corresponding safety population. Frequency counts and percentages of patients excluded by

primary reason for exclusion will be provided for patients who failed to meet study entry requirements during screening.

Frequency counts and percentages of patients who complete the study treatment or discontinue early from the study, along with their discontinuation reasons and whether they completed follow-up or enrolled into the extension, will be summarized. A by-treatment summary will provide for the DBW period with the DBW safety population.

A listing of patient disposition will be provided for all enrolled patients, with the extent of their participation in the study and the reason for discontinuation. A listing of all randomized patients with their treatment assignment will also be provided.

6.7. Patient Characteristics

Patient characteristics including demographics, baseline characteristics, historical illnesses, and preexisting conditions will be summarized descriptively at the study baseline by treatment periods with the corresponding analysis population. They will also be summarized descriptively by treatment group for the DBW period with the DBW population. No formal statistical comparisons will be made among treatment groups unless otherwise stated.

[Table JAHV.6.2](#) describes the specific variables and how they may be summarized.

Table JAHV.6.2. Patient Characteristics

Variable	Continuous measure Summary	Categorical Summary
Age ^a	Yes	12 to <18 years, 9 to <12 years, 6 to <9 years, and 2 to <6 years
Sex	No	Male, Female
Race	No	American Indian/Alaska Native, Asian, Black/African American, Native Hawaiian or other Pacific Islander, White, or Multiple
Geographic region	No	By Country
	No	Asia, South America, Europe and rest of world
Height (cm)	Yes	None
Weight (kg)	Yes	None
BMI ^b	Yes	Underweight (<18.5 kg/m ²), Normal (≥18.5 and <25 kg/m ²), Overweight (≥25 and <30 kg/m ²), Obese (≥30 and <40 kg/m ²), Extreme obese (≥40 kg/m ²)
Tobacco use	No	Never, Current, Former
Prior biologic JIA therapy ^c	No	Never used, Ever used
Number of prior biologics JIA ^c	No	0, 1, 2, >2
Prior non-biologic JIA therapy ^d	No	Never used, Ever used
Number of non-biologic JIA therapies ^d	No	0, 1, 2, >2
MTX usage at baseline	No	Yes, No
Duration of JIA diagnosis (years) ^e	Yes	0 to <2 years, 2 to <5 years, 5 to <10 years, ≥10 years
Age at JIA onset (years) ^e	Yes	12 to <18 years, 6 to <12 years, and 2 to <6 years
Baseline number of active joints	Yes	None
Baseline number of joints with limited range of motion	Yes	None
Baseline Physician's Global Assessment of Disease Activity	Yes	None
Baseline Parent's Global Assessment of Patient's Overall Well-Being	Yes	None
Baseline Physical function measured by CHAQ	Yes	None
Baseline ESR	Yes	Elevated (above 20 mm/L) or Not Elevated (not above 20 mm/L)
Baseline hsCRP	Yes	above 3 mg/L or not above 3 mg/L
Baseline Juvenile Arthritis Disease Activity Score (JADAS)-27	Yes	None
Baseline Physical Summary Score (PhS) and Psychosocial Summary Score (PsS) of the Child Health Questionnaire-Parent Form 50 (CHQ-PF50)	Yes	None
Baseline caregiver burden as measured by Parental Impact-Time and Parental Impact-	Yes	None

Variable	Continuous measure Summary	Categorical Summary
Emotion scales of the CHQ-PF50		
Baseline Arthritis-related pain measured by CHAQ pain severity	Yes	None
Variable	Continuous measure Summary	Categorical Summary
Baseline SPARCC ^{f, g}	Yes	None
Baseline JSpADA ^{f, g}	Yes	None
Baseline PASI score ^f	Yes	None
Latest screening period renal function status	No	impaired (eGFR <60 mL/min/1.73 m ²) or not impaired (eGFR ≥60 mL/min/1.73 m ²)
Immunoglobulin level (Including T and B cells, T cell subsets and NK cells)	Yes	None
Peripheral blood immunophenotyping (Including T and B cells, T cell subsets and NK cells)	Yes	None
pre-vaccination IgG titer ^h	Yes	None

Abbreviations: BMI = body mass index; CHAQ = Childhood Health Assessment Questionnaire; CHQ-PF50 = Child Health Questionnaire-Parent Form 50; ESR = erythrocyte sedimentation rate; IgG = immunoglobulin G; JIA = juvenile idiopathic arthritis; JSpADA = Juvenile Spondyloarthritis Disease Activity Index; NK = natural killer; PASI = Psoriasis Area and Severity Index; SPARCC = Spondyloarthritis Research Consortium of Canada.

- a Age in years will be calculated as length of the time interval from the imputed date of birth (July 1st in the year of birth collected in the electronic case report form (eCRF)) to the informed consent date.
- b Body Mass Index (BMI) will be calculated as: $BMI (kg / m^2) = Weight (kg) / (Height (m))^2$.
- c Biologic JIA therapies for example: anakinra, canakinumab, tocilizumab, sarilumab, rituximab, etanercept, adalimumab, abatacept, tocilizumab, and golimumab
- d Non-biologics JIA therapies for example: methotrexate, celecoxib, diclofenac, ibuprofen and corticosteroids.
- e Age at diagnosis in years will be calculated as the time interval from the imputed date of birth (July 1st in the year of birth collected in the eCRF) to the date of JIA diagnosis.
- f For JPsA patients who have this score available.
- g For ERA patients who have this score available.
- h In patients eligible for vaccination with tetanus, diphtheria, and pertussis (TDaP) and/or pneumococcal conjugate vaccine according to local guidelines.

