6.1. Inclusion Criteria

Patients are eligible to enroll in the study only if they meet all of the following criteria at screening and at baseline:

Patient and Disease Characteristics

- [1] Are at least 2 years and less than 18 years of age; full date of birth will be collected except in countries in which it is not allowed.
- [2] Have a diagnosis with onset before the age of 16 years of any of the following forms of JIA as defined by ILAR criteria:
 - Polyarticular JIA (positive or negative for RF)
 - Extended oligoarticular JIA
 - ERA
 - JPsA
- [3] Have had an inadequate response or intolerance to treatment with ≥ 1 conventional or bDMARD. Patients must have been treated for at least 12 weeks before inadequate response may be determined.
- [4] Patients with polyarticular JIA or extended oligoarticular JIA must have at least 5 active joints at screening and baseline. Those with JPsA must have at least 3 active joints at screening and baseline. Those with ERA must have (a) at least 3 active joints at screening and baseline or (b) involvement of at least 1 sacroiliac joint AND a physician global assessment of at least 3 (on the 21-circle numeric rating scale [NRS]). Active joint is defined as the presence of joint swelling or, in the absence of swelling, joints with limitation of motion plus pain on motion and/or tenderness on palpation.

Informed Consent

- [5] Both the child or adolescent and a parent or legal guardian are able to understand and fully participate in the activities of the clinical study and sign their assent and consent, respectively, accordance to local guidelines.

Contraception

- [6] Male or nonpregnant, nonbreastfeeding female patients

Patients of child-bearing potential who are abstinent (if this is complete abstinence, as their preferred and usual lifestyle).

Total abstinence is defined as refraining from intercourse during the entirety of the study and for at least 1 week following the last dose of investigational product. Periodic abstinence such as calendar, ovulation, symptothermal, post-ovulation methods and withdrawal are not acceptable methods of contraception.

Otherwise, patients and their partners of childbearing potential must agree to use 2 effective methods of contraception, where at least 1 form is highly effective for the entirety of the study and for at least 1 week following the last dose of investigational product.

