10.3.4.3. Vital Signs, Physical Findings, and Other Safety Evaluations

Vital signs will be presented as mean changes from baseline and as incidence of abnormal values. Other data, including body weight and height data will be summarized. Weight, height, and BMI data will be merged to the Center for Disease Control standard growth data by age and gender to compare subjects' growth with the standard. Other measures related to growth velocity (e.g., occipital circumference measurement) will be evaluated. Further analyses may be performed.

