6.18.4.1. Standardized Growth

Weight, height, and BMI data will be merged to the Centers for Disease Control and Prevention (CDC) standard growth data (released in 2000) by age and gender in order to compare patients’ growth with the standard. Z-score and standardized percentile of weight, height, and BMI at each visit will be calculated based on the 2000 CDC growth charts.

The z-score and percentile calculations are based on algorithms and data provided by the National Center for Health Statistics. The details are provided in the CDC website (<https://www.cdc.gov/nccdphp/dnpao/growthcharts/resources/sas.htm>).

- The following summaries will be provided by treatment period with the corresponding safety population: baseline, mean change of actual measure, z-score and standardized percentile of weight, height, and BMI will be summarized.
- Patients’ mean weight, height, and BMI standardized percentile will be plotted versus investigational product exposure time.

By-patient listings of actual measures, z-scores, standardized percentiles in weight, height, and BMI for each visit will be provided.

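### The baseline BMI categories in SAP Table JAHV.6.2 ignore age and sex, so many normal-weight young children would be tabulated as underweight, although CDC BMI-for-age percentiles are already planned

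*SAP*

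**What the plan says.** Protocol 6.1 admits patients who "Are at least 2 years and less than 18 years of age". SAP 6.7, Table JAHV.6.2, lists the baseline characteristics. Its age row has four bands, "12 to <18 years, 9 to <12 years, 6 to <9 years, and 2 to <6 years". Its BMI row is summarised both continuously and in five categories, beginning "Underweight (<18.5" and "Normal (≥18.5 and <25" kg/m2 and continuing with limits at 30 and 40. Footnote b defines BMI only as weight in kg divided by the square of height in metres. Nothing in the row or its footnote varies the limits by age or sex, and no reason is given for fixed limits.

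SAP 6.18.4.1 handles the same measure differently: "Z-score and standardized percentile of weight, height, and BMI at each visit will be calculated based on the 2000 CDC growth charts", using "standard growth data (released in 2000) by age and gender". Protocol 10.3.4.3 plans the same comparison: "Weight, height, and BMI data will be merged to the Center for Disease Control standard growth data by age and gender". Neither section defines weight-status bands.

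**The concern.** A fixed BMI limit can describe weight status only if the usual BMI is much the same at every age classified. The SAP's own growth section treats BMI as something to be read against age and sex. Elsewhere the SAP also allows for age: Table JAHV.6.14 sets blood pressure and pulse limits in four age groups, and Table JAHV.6.18 uses paediatric lipid limits with triglycerides split by age. The BMI row is the exception.

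What is at stake is how the baseline table reads. Growth is a monitored safety topic here (Protocol 9.4.6.2). A reader could see many young children counted as underweight when their BMI is ordinary for their age. Because the category would largely follow age, an age difference between randomised arms could also look like a difference in weight status.

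**Working it through.** The plan states no figure for this row, so there is nothing to reproduce. Two checks were made.

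**1. Arithmetic from the documents alone.** With BMI = weight / height², the weight at which the *Underweight* label stops applying is 18.5 × height²:

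- 100 cm: 18.5 × 1.00² = 18.5 kg
- 110 cm: 18.5 × 1.10² = 22.4 kg
- 120 cm: 18.5 × 1.20² = 26.6 kg

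Protocol Appendix 6 uses an 18 kg threshold for children under 8 years. The height at which 18 kg gives a BMI of 18.5 is √(18 / 18.5) = 0.986 m. Every child below 18 kg and taller than 98.6 cm is therefore labelled underweight.

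**2. Share of young children labelled underweight.** This needs a paediatric BMI distribution, which the documents do not contain. Assumption: lognormal, median *m* from 15 to 18 kg/m2, log-SD *s* from 0.08 to 0.15, with normal weight taken as the 5th to 85th percentile.

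- All children: P = Φ(ln(18.5 / *m*) / *s*)
- Normal-weight children: [min(P, 0.85) − 0.05] / 0.80

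| Assumed median (kg/m2) | All children, *s* = 0.08 | All children, *s* = 0.15 | 5th–85th percentile, *s* = 0.08 | 5th–85th percentile, *s* = 0.15 |
|---|---|---|---|---|
| 15 | >99% | 92% | 100% | 100% |
| 16 | 97% | 83% | 100% | 98% |
| 17 | 85% | 71% | 100% | 83% |
| 18 | 63% | 57% | 73% | 65% |

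Worked example, *m* = 18 and *s* = 0.15: ln(18.5 / 18) / 0.15 = 0.18, so P = 0.57 and the normal-weight share is (0.57 − 0.05) / 0.80 = 0.65.

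The normal-weight share falls to one half when P = 0.45, that is at a median of 18.5 × exp(0.126 × *s*): 18.7 kg/m2 for *s* = 0.08 and 18.9 kg/m2 for *s* = 0.15. A majority is mislabelled unless the true median in young children exceeds about that value.

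For contrast, a line drawn at the 5th percentile of an age- and sex-specific reference puts about 5% of reference children below it at every age, by definition.

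**The case against.** The strongest reply is that little depends on this row. SAP 6.7 presents the table as a way the variables may be summarised and plans no formal comparison between groups. BMI category is not a randomisation stratum (SAP 5.3), a covariate (SAP 6.2) or a listed subgroup (SAP 6.16). BMI is also summarised continuously in the same row, and age-standardised BMI is reported under SAP 6.18.4.1. All of this stands, and it limits the consequence to presentation. It does not make the labels apt for young children.

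Three stronger readings are tempting, and the documents do not support them:

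- *The SAP requires baseline BMI to be categorised against the CDC standard.* Section 6.18.4.1 says only that growth data will be merged with that standard for the safety summaries. It sets no rule for the baseline table.
- *The growth assessment would be wrong, or the SAP's tables would contradict each other.* The growth summaries use z-scores and percentiles and do not draw on this row. Section 6.18.4.1 defines no weight-status categories, so no two specified outputs give opposing classifications.
- *Most patients in the trial would be labelled underweight.* The documents give no expected age mix. The only age-specific numbers are the 5 to 8 patients per group in the Safety/PK period (Protocol 5.1.2). When amendment (d) was written, Appendix 7 showed direct OLLI enrolment only for ages 9 to under 18. The number of patients affected is unknown.

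Nor do the documents call the limits adult ones. What they show is that the limits are fixed across age and sex.

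**Conclusion.** The point holds as a minor one. As written, Table JAHV.6.2 classifies the BMI of children from age 2 by limits that take no account of age or sex, while the means to do better are already in the SAP. The height-and-weight examples follow from the documents alone. The shares of about 57% to over 99% of all young children, and about 65% to 100% of those in the 5th to 85th percentile band, are conditional on the assumed lognormal distribution with median 15 to 18 kg/m2 and log-SD 0.08 to 0.15. They describe young children under that assumption and do not forecast trial counts. The harm is a misleading row in a descriptive table. The primary analysis, power, alpha, safety inference and the planned growth summaries are unchanged.

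**What to change.** In Table JAHV.6.2, replace the five BMI categories with bands of the CDC BMI-for-age percentile (or z-score). Compute them at study baseline with the Section 6.18.4.1 algorithm and write the chosen band limits into the table. Keep the continuous BMI summary.

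The cost is one row to respecify and no new data. Two details need attention. Section 6.18.4.1 supplies percentiles but no band limits, so these must be chosen and stated. Its outputs are also tied to the safety populations and the safety baseline in Table JAHV.6.10, whereas Table JAHV.6.2 uses the analysis populations at study baseline, so the algorithm should be applied to the study-baseline values.

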5.1.1. Screening and Baseline Periods

The duration of the Screening Period is up to 42 days prior to baseline. At screening, the parent or legal guardian will sign the informed consent form (ICF) and the patient will sign the assent form (as applicable) per local requirements prior to any study assessments, examinations, or procedures being performed ([Appendix 3](#)). All screening procedures will be performed according to the Schedule of Activities (Section 2).

Patients who receive a purified protein derivative (PPD) skin test at screening will need to return within 48 to 72 hours later to read the skin test. Treatments with concomitant JIA therapies during the study is permitted only as described in Section 7.7. Patients will remain on background cDMARDs, oral corticosteroid, NSAIDs, and/or analgesics if patients are on stable doses of these treatments at screening (Sections 6.2 and 7.7). Patients who have previously been treated with bDMARDs are eligible for the study. However, treatment must have been discontinued 4 weeks prior to screening for TNF inhibitors, IL-1 inhibitors, IL-6 inhibitors, or abatacept and 6 months prior to baseline for rituximab.

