7.1. Treatments Administered

This study involves a comparison of baricitinib dose, by age (4-mg for children ≥ 9 years of age and adolescents 12 to < 18 years of age and 2-mg for children < 9 years of age as the starting dose; see Appendix 7 for updated dosing based on the current data), with placebo in the DBW period. The dosages will be adjusted if the interim analyses after the Safety/PK period demonstrate that the profiles are not comparable with the target PK or safety profiles in adults. Therefore, a 1-mg dose is described in [Table JAHV.5](#) should this be needed.

Baricitinib will be dosed as tablets or oral suspension QD based on the age of the patient at Visit 2 (for patients enrolled in the Safety/PK portion) and at Visit 5 (for all other patients); formulation will not change during the study. Baricitinib should be taken with sufficient water or fluid to allow easy swallowing of the medication. All patients < 6 years of age will receive oral suspension. Patients ≥ 6 to < 12 years old have the option of receiving the oral suspension. Patients > 12 years old will be supplied tablets. Based on PBPK modeling, initial doses will be 4-mg for adolescents 12 to < 18 years old and in children ≥ 9 to < 12 years old, and 2-mg in children < 9 years old to produce exposures similar to those in adults after 4-mg QD administration. Refer to Section 5.5 for additional information. [Table JAHV.5](#) shows the treatment regimens.

Table JAHV.5. Treatment Regimens

Treatment Group	Treatments Administered	
	Safety/PK and OLLI Period	DBW Period
Baricitinib 4-mg	Baricitinib 4-mg oral QD tablet Baricitinib 2-mg/mL oral suspension	Baricitinib 4-mg oral QD tablet Baricitinib 2-mg/mL oral suspension
Baricitinib 2-mg	Baricitinib 2-mg oral QD tablet Baricitinib 2-mg/mL oral suspension	Baricitinib 2-mg oral QD tablet Baricitinib 2-mg/mL oral suspension
Baricitinib 1-mg	Baricitinib 1-mg oral QD tablet Baricitinib 2-mg/mL oral suspension	Baricitinib 1-mg oral QD tablet Baricitinib 2-mg/mL oral suspension
Placebo comparator	N/A	Baricitinib 4-mg placebo oral QD tablet Baricitinib 2-mg placebo oral QD tablet Baricitinib 1-mg placebo oral QD tablet Baricitinib 2-mg/mL placebo oral suspension

Abbreviations: DBW = double-blind withdrawal; eGFR = estimated glomerular filtration rate; N/A = not applicable; OLLI = open-label lead-in; PK = pharmacokinetics; QD = once daily.

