6 to <9 years old	Safety/PK enrollment completed as of October 2020	2 mg (based on predicted data – to be confirmed with observed data)
2 to <6 years old	Safety/PK to be initiated	2 mg ^a

Abbreviations: OLLI = open-label lead-in; PK = pharmacokinetic;

^a To be confirmed after evaluating data from patients aged 6 to <9 years.

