6.11.1. X-ray and Structure Data

Semiannual wrist, hand, finger, and knee radiographs to monitor bone age and long bone growth. Imaging will be required until skeletal maturity is attained, and this should be determined by a qualified physician at the site. For patients already enrolled at the time of protocol amendment (d), the x-ray procedures will be optional. For patients that consent to the x-ray procedures, x-rays must be completed within 30 days from time of consent/assent and every 6 months \pm 30 days thereafter.

Descriptive statistics will be used to summarize the modified total Sharp score (mTSS) (when data are available), skeletal age, and chronological age at baseline for all the patients who have a baseline value available.

For patients in the DBW period, an analysis of covariance model with baseline mTSS, presence of erosion at baseline (yes or no), and treatment group in the model will test the treatment difference between baricitinib and placebo in change from baseline to Week 44 in mTSS when data are available. Linear extrapolation will be applied for patients who are missing the radiograph at Week 44 but who have baseline and postbaseline radiographs available.

The skeletal age can deviate from the chronological age calculated from the date of birth. Results will include a description of the skeletal age, the chronological age, and the difference between skeletal age and chronological age at baseline and post baseline when data are available.

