6.16. Subgroup Analysis

Cox proportional hazards regression will be used to evaluate the similarity of treatment effect across the JIA categories (polyarticular and extended oligoarticular [combined] versus ERA and JPsA [combined]). The model will have treatment and stratification variables as factors in the model. If any of these variables are redundant for a particular model, they will be dropped.

For the primary endpoint, selected secondary endpoints, and selected growth measurements, following subgroup analysis may be conducted:

- Gender: (Male; Female)
- Age group (12 to <18 years, 9 to <12 years, 6 to <9 years, 2 to <6 years)
- Geographic region (Asia, South America, Europe and rest of world)
- JIA categories (polyarticular and extended oligoarticular [combined] versus ERA and JPsA [combined])
- JIA categories (polyarticular, extended oligoarticular, ERA, JPsA)
- Predose exposure ESR categories (elevated [>20 mm/hour] and not elevated)
- history of prior bDMARD use (Yes or No)
- MTX usage at baseline (Yes or No)

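### The SAP counts every child's age from 1 July of the birth year to consent, which puts about 5% to 6% of children in the wrong age band or in none

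*SAP*

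**What the plan says.** SAP 6.7, Table JAHV.6.2, summarises age as a continuous variable and in four bands, "12 to <18 years, 9 to <12 years, 6 to <9 years, and 2 to <6 years". Note a fixes both ends of the interval used for age: "imputed date of birth (July 1st in the year of birth collected in the electronic case report form (eCRF)) to the informed consent date". The wording sets a general rule, not a fallback for missing dates. Note e of the same table applies the same imputed date to age at diagnosis.

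SAP 6.16 lists the same bands as an optional subgroup, "Age group (12 to <18 years, 9 to <12 years, 6 to <9 years, 2 to <6 years"), for the primary endpoint, selected secondary endpoints and selected growth measurements. It gives no other definition of age.

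The protocol differs on both dates:

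- Birth date: in Protocol 6.1, criterion 1, "full date of birth will be collected except in countries in which it is not allowed".
- Reference date: Protocol 7.1 sets tablets or suspension by age at Visit 2 for the Safety/PK cohort and at Visit 5 for the rest. Protocol 5.1.1 adds: "The duration of the Screening Period is up to 42 days prior to baseline".

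The four bands are the protocol's dosing age groups. Protocol Appendix 7 gives 4 mg at 9 to <12 and 12 to <18 years, and 2 mg in the two younger groups. The 2 mg dose at 6 to <9 is still "to be confirmed with observed data".

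**The concern.** The SAP takes over the dosing age groups but fills them using a different birth date and a different reference date. It replaces a birth date that the protocol mostly collects with one that can be half a year off, and it stops the clock at consent instead of first dose. Children near 6, 9 or 12 can be counted in a neighbouring band. Eligible children just over 2 or just under 18 can get an age that fits no row.

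At stake is whether the age table describes the groups that were dosed, and whether any age subgroup built on it does.

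**Working it through.** The documents state no misclassification figure, so there is none to reproduce.

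**Inputs from the documents.** Cuts at 2, 6, 9, 12 and 18 years; consent up to 42 days before baseline; 197 patients entering the open-label lead-in (SAP 5.2), used only to scale counts.

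**Assumptions, not in the documents.** Birthdays and visits are spread evenly over the year, and consent is 1 to 42 days before first dose, evenly. There are three age mixes of 197: even over 2 to <18; 8/12/25/152; and 25/30/40/102 (2 to <6, 6 to <9, 9 to <12, 12 to <18). Ages are even within each band.

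**Error in age.** SAP age = age at first dose + e - L. Here e is the true birth date minus 1 July (even over -0.5 to +0.5 year) and L is the gap from consent to first dose.

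- Range: -0.5 - 42/365.25 = -0.61, to 0.5 - 1/365.25 = +0.50 year.
- Mean of L = 21.5/365.25 = 0.0589.
- Mean of L² = (1 + 42 + 42²)/(3 × 365.25²) = 0.0045.

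**Crossing a cut.** Let D be the mean downward overshoot and U the mean upward overshoot.

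- D = (0.25 + 0.0589 + 0.0045)/2 = 0.1567.
- U = (0.25 - 0.0589 + 0.0045)/2 = 0.0978.
- Share crossing an inner cut = (share per year of age just above) × D + (share per year just below) × U.
- Share outside all bands = (share per year just above 2) × D + (share per year just below 18) × U.

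Example, cut at 9, mix 8/12/25/152: (25/197/3) × 0.1567 + (12/197/3) × 0.0978 = 0.0066 + 0.0020 = 0.86%.

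| Mix | Cut 6 | Cut 9 | Cut 12 | No band | Total | Of 197 |
|---|---|---|---|---|---|---|
| Even | 1.59% | 1.59% | 1.59% | 1.59% | 6.36% | 12.5 |
| 8/12/25/152 | 0.42% | 0.86% | 2.43% | 1.42% | 5.13% | 10.1 |
| 25/30/40/102 | 1.11% | 1.56% | 2.01% | 1.34% | 6.02% | 11.9 |

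A simulation on the same assumptions gives totals of 6.4%, 5.1% and 6.0%.

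Two sensitivities:

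- Protocol 6.1 requires age 2 or more at screening as well as at baseline. Dropping children still under 2 at consent replaces D by 0.5²/2 = 0.125 at the cut at 2. The no-band share becomes 1.2% to 1.4% and the total 5.1% to 6.2%.
- A quarter of children in each band would give 6.9% in total and 2.1% across age 9.

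**Which part of the rule matters.** With the true birth date but still the consent date, a child can only cross downwards, by L. Even mix: 4 cuts × (1/16) × 0.0589 = 1.5%; the other mixes give 1.2% and 1.4%. The 1 July date is therefore the main source. With the true birth date at Visit 2 or 5 the mismatch is zero by construction.

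**Worked cases.**

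- Born 5 Jan 2012, consent 20 Jan 2021, Visit 5 on 20 Feb 2021: true age 9.13 (4 mg), SAP age 8.56.
- Born 20 Dec 2011, consent 1 Aug 2020, Visit 5 on 29 Aug 2020: true age 8.69 (2 mg), SAP age 9.09.
- Born 15 Jan 2019, consent 1 Mar 2021: true age at consent 2.12, SAP age 1.67 (no band).
- Born 20 Nov 2003, consent 1 Sep 2021: true age at consent 17.78, SAP age 18.17 (no band).

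**The case against.** A reader might infer more than the documents support. Four limits stand.

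- **Safety by age.** The SAP specifies no adverse event or laboratory table by these bands. SAP 6.16 is optional, and adverse events come within its reach only because Table JAHV.4.2 lists them among the secondary endpoints. SAP 6.18 leaves some detail to compound-level standards that are not in the documents. A claim that planned safety results would be wrong cannot be sustained.
- **Dose.** The cuts at 6 and 12 do not change the dose, so most of the misplaced children are not on the wrong side of a dose boundary. Age band is not dose in any case: Protocol 7.4 and 7.7 halve the dose for eGFR below 60 mL/min/1.73 m² and for strong OAT3 inhibitors. The Protocol 7.1 sentence on Visit 2 and Visit 5 literally governs tablet or suspension. Using the same date for dose is reasonable but inferred.
- **Growth.** SAP 6.18.4.1 calculates z-scores at each visit, which needs age at each visit. Note a gives one age at consent, so it cannot be the age used there. SAP 6.11.1 says "The skeletal age can deviate from the chronological age calculated from the date of birth", which may mean that note a is confined to the characteristics table. Nothing shows that growth z-scores would be wrong.
- **Data held.** Note a refers to a year of birth in the eCRF. If the analysis data hold only the year, the full date is not available to the programmer.

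None of this changes what note a says. It is a stated rule, it applies to every child, and it departs from the date of birth that the protocol says is collected.

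**Conclusion.** The point holds in a limited form. Followed as written, note a puts about 5% to 6% of children (10 to 13 of 197) in the wrong age band or in none. Of all children, 1.3% to 1.6% get an age outside 2 to <18, and 0.9% to 1.6% (about 2 to 3 of 197) fall on the wrong side of 9. About 94% to 95% stay in the right band.

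The effect falls on the demographic age table and, if it is programmed from the same age, on the optional age subgroups in SAP 6.16. Age is not a randomisation stratum and does not enter the primary log-rank test, so the primary result and the pooled and by-arm results are unaffected.

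The sizes rest on assumed age mixes, even birthdays and a consent gap of 1 to 42 days. They also assume that the dosing age group was set from the true date of birth at Visit 2 or 5. The documents do not say how many countries bar the full date.

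**What to change.** In Table JAHV.6.2 note a, and for the age groups in SAP 6.16, compute age at Visit 2 (Safety/PK cohort) or Visit 5 (all others) from the full date of birth. Impute 1 July only where the full date is not available, and in those children take the band from the age group used to dispense the dose. State that the same birth date, with age at each visit, is used for the CDC z-scores and for chronological age in 6.11.1.

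The cost is one derivation, with no new visits or tests. Children with only a birth year keep an imputed age, so precision is mixed. If the eCRF holds only the year throughout, the bands must come from site or dispensing records, which is more work.
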